6.1.3 Protocol Deviations

A protocol deviation is any change, divergence, or departure from the study design or procedure defined in the protocol.

A subset of the protocol deviations can be identified as a major protocol deviation as described below:

Major Protocol Deviation: A major protocol deviation that might significantly affect the completeness, accuracy, and/or reliability of the study data or that might significantly affect a subject's rights, safety, or well-being. Important deviations include includion/exclusion criteria violations, cases where withdrawal criteria developed but the subject was not withdrawn, receiving the wrong treatment or incorrect dose, and receiving excluded concomitant medications.

Upon soft lock of database, all documented protocol deviations in the study will be reviewed to identify all important protocol deviations by a data review team including representatives from clinical operations, medical, data management, and statistics, and sent to the sponsor for approval. Final decisions will be documented and databased.

Protocol deviations will be listed by subject with major deviaitons flagged.

6.1.4 Medical and Surgical History

Medical history at Screening Visit (prior conditions and present conditions) will be tabulated using version 15.0 of the Medical Dictionary for Regulatory Activities (MedDRA®) by System Organ Class and Preferred Term, both with a summary of incidence by diagnosis and the proportion with any abnormality. A by-subject listing will be created.

6.1.5 Prior and Concomitant Medications

Prior and concomitant medications will be coded using the World Health Organization Drug Dictionary (WHODD) March 2012. These will be summarized overall and by Safety Group based on Anatomical Therapeutic Chemical Class 3 level (ATC 3), using incidence and percentage.

Neurological and anti-spasticity concomitant medications, identified before data lock, will be summarized separately overall, and for each Safety Group using incidence and percentage, and will be listed for all subjects.

Medications previously used (within 30 days of Visit 1) and before the on-study treatment will be considered Prior Medications. These will be summarized separately.

Physical therapy regimen will be summarized by visit using counts and percentages. Numbers of subjects with changes at post-baseline visits will also be summarized.

When medication start and/or stop dates are missing, the following imputations will be made (subject to medical review):

Missing Medication Start Dates

- 1. If onset date is completely missing, then onset date is set to date of first dose
- 2. If year is present and (month and day are missing), or (month is missing but day is present):
 - a. If year = year of first dose, then set date to first dose date

- b. If year < year of first dose and medication stop month and year are available, then set to first of the end month
- c. Otherwise if year < year of first dose, then set month and day to December 31st.
- d. If year > year of first dose, then set month and day to January 1st.
- 3. If month and year are present and day is missing:
 - a. If year=year of first dose and
 - i. If month = month of first dose then set day to day of first dose date
 - ii. If month < month of first dose then set day to last day of month
 - iii. If month > month of first dose then set day to first day of month
 - b. If year < year of first dose then set day to last day of month
 - c. If year > year of first dose then set day to first day of month
- 4. If the medication start date is completely missing and the corresponding stop date is completely missing, the medication start date will remain missing.

• Missing Medication Stop Dates

If the stop date is completely missing, the stop day will not be estimated (i.e., the medication will be assumed to be continuing).

If only the day of Medication stop is unknown, the day will be assumed to be the last day of the month (e.g. ??-JAN-2011 will be treated as 31-JAN-2011).

A by-subject listing comprehensive of prior and concomitant medications will be generated, inclusive of verbatim and coded terms, doses and routes, and start and stop dates. Prior medications will be flagged. Prior and concomitant status with respect to study drug treatment will be determined based on imputed dates as defined above.

6.1.6 Exposure and Compliance

6.1.6.1 *Exposure*

Exposure data at each visit starting with Screening will be summarized overall and for each of the safety groups. Specifically, the numbers of subjects for each dose level will be summarized with counts and percentages, and descriptive summaries (mean, median, mode, and standard deviation) of dose at each visit will be provided.

For each subject, total exposure duration will be calculated as the number of days the subject

The exposure duration will be calculated as the date of last dose reported on the final status eCRF— date of first dose + 1. In cases where the date of last dose is not reported or missing, the date of last dose will be considered the date of the last visit with drug return reported. If no visit with drug return reported exists, exposure duration will be set to 1 day.

This exposure data will be summarized overall for the safety population, and by each of the three safety groups described in Section 5.1.2.

Individual subject listings will be prepared.

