## Statistical methods:

Descriptive statistics, including the numbers, means, standard deviations, medians, minimums, maximums and 95% confidence intervals for continuous variables and the numbers and percentages for categorical variables, will be provided. Listings of individual subject's data will also be produced.

Subset analysis will be stratified by concomitant anti-spasticity and MS medication used if the percentage of subjects in these stratification groups is  $\geq 10\%$  of the total number of subjects enrolled.

Confidential Page 4 of 47

	Day -14	Day 1	Day 28	Day 84	Day 182	
Activities	Week -2 Visit 1 (Screen) a	Week 1 Visit 2 (Baseline)	Week 4 ± 5 days Visit 3	Week 12 ± 5 days Visit 4	Week 26 ± 5 Days Visit 5 / Premature Termination Visit b	Visits Every 3 Months ± 5 days c
Informed consent	X	-	-	-	-	
Medical history and demographics	X	-	-	-	-	
Physical examination	X	-	-	-	X	
Neurologic examination	X	-	-	-	X	
Urine pregnancy test	X	-	X	X	X	X
Vital signs (sitting)	X	-	X	X	X	
Clinical laboratory tests d	X	-	-	-	X	
12-lead ECG e	X	-	X	X	X e	
C-SSRS	X	-	X	X	X	X
Concomitant medication and physical therapy assessments	X	X	X	X	X	X
AE evaluation	X	X	X	X	X	X
Dispense study medication	X	X	X	X	X	X
Collect study medication	-	X	X	X	X	X
Dispense / collect subject diaries	X	X	X	X	X	X
6 1 1 1 · · · · ·	77	37	7.7	7.7	77	***

Table 1: Visits and Procedures Schedule

X

X

Χ

X

X

X

Schedule next visit

Confidential Page 5 of 47

aScreening Visit assessments in CLR\_11\_04 which are identical to final visit assessments in CLR\_09\_21 do not need to be repeated. The Screening Visit may be completed simultaneously with the final visit for CLR\_09\_21, and on the following day, if needed, provided drug supply from CLR\_09\_21 does not run out. Subjects cannot enter CLR\_11\_04 if drug supply runs out prior to the completion of the screening process.

<sup>bFor subjects not completing the study, all activities scheduled at this visit are to be conducted during the Premature Termination visit with the exception of the ECG (see footnote "e" below) and the physical and neurologic examinations. These three assessments may be conducted during the Premature Termination visit as needed in order to follow the resolution of any adverse events.

<sup>cThese visits will be scheduled 90 (± 5) days following the previous visit.

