# 9.5. Treatment Compliance

Treatment compliance will be measured on the basis of a capsule count by the investigator or his/her designee every time drug supplies are returned. Each subject will be instructed to bring the study medication (with the capsules that remain) with him/her to the next scheduled visit. If the subject fails to bring the study medication on the designated day, he/she will be told to bring the study medication within the next 3 days. If the subject fails to do so, the capsule count will be recorded as "not available."

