3.2 Study Design

This is a multicenter, open-label, safety study in subjects with spasticity due to MS. Approximately 550 subjects will be enrolled in approximately 35-40 centers, in order to obtain safety data from at least 250 subjects who have completed at least 26 weeks of treatment and at least 200 subjects who have completed at least 1 year of treatment.

Subjects	enrolled	in clin	ical trial	CLR_(9_21	who co	mplete					
			that	trial wi	ll be e	ligible 1	to partic	ipate ir	this	trial.	In a	addition,
subjects	not enrol	led in	trial CLI	R 09 21	who	are on	a stable	daily	dose			
as well as	S	naïve	subjects	will be	eligibl	e to par	ticipate i	in this 1	rial.			

Informed consent will be obtained from subjects prior to the initiation of any trial-specific procedures.

A Subject Diary (Appendix 1) will be utilized to assess compliance and collect comments regarding any important problems or issues (missed dose, reason for missing dose, disturbing signs/symptoms, etc) associated with this trial. The clinic staff will review the diary during each visit. Comments that may suggest adverse events (AEs) will be reviewed with the subject to determine the presence of AEs. Any missed doses will be recorded in the diary, along with the reason for the missed dose. The diary will help confirm the level of drug compliance in this study.

30Oct2017

Visits are scheduled on: Days -14 (Week -2), 1 (Week 1), 28 (Week 4), 84 (Week 12), 182 (Week 26), and during 3 month interval, follow-up visits.

Table 1 in Section 3.2.3 presents the visit and procedures schedule.

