5.4 Interim Analysis

For regulatory purposes, interim reports of safety data accrued will be prepared annually. Post-trial AEs not included in the trial safey database will be included in a separate pharmacovigilance database, which will be used for generating periodic safety reports. No formal interim analyses are planned for the study.

30Oct2017

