Adverse events will be listed for all subjects, including verbatim and coded terms, duration, severity, and relationship to the study drug. TEAE status will be determined based on the imputed dates as defined above.

The incidence and proportion of subjects with TEAEs and SAEs will be summarized by System Organ Class and Preferred Term overall and by the Safety Groups defined in Section 5.1.2.

An overview of TEAEs will be provided that summarizes the incidence of subjects with one or more AE, the incidence of AEs by highest relationship, the incidence of AEs by highest severity, the incidence of AEs by action taken, the incidence of AEs outcome, the incidence of serious adverse events (SAEs), and the incidence of AEs by type of seriousness.

The incidence and proportion of subjects with TEAEs and SAEs will also be summarized overall and by Safery Groups as follows:

- TEAE by System Organ Class, and Preferred Term
- TEAEs by Preferred Term, in descending order of frequency
- TEAEs by highest severity
- TEAEs by highest relationship
- Treatment-related (defined as at least possibly related) TEAEs by System Organ Class, and Preferred Term
- TEAEs resulting in discontinuation from the study
- Treatment-related (defined as at least possibly related) TEAEs by System Organ Class, and Preferred Term, and severity
- TEAEs by dose at time of onset
- TEAEs by time of onset windows, where the denominator for each visit window is the total number of subjects with exposure to drug as of the first day of the window, defined as:

- Treatment Emergent SAE by System Organ Class and Preferred Term
- Treatment Emergent Fatal SAE by System Organ Class and Preferred Term
- Treatment-related SAE by System Organ Class, Preferred Term, and Severity

TEAEs will also be summarized by subgroups as described in Section 6.4.

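### SAP 6.1.6.1 sets exposure to 1 day when the last-dose date is missing and no drug return is recorded, even if the trial's own dosing and visit records show months of treatment

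*SAP*

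**What the plan says.** SAP 6.1.6.1 defines exposure in three steps.

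1. "The exposure duration will be calculated as the date of last dose reported on the final status eCRF", minus the date of first dose, plus 1.
2. If the last-dose date is missing, "the date of last dose will be considered the date of the last visit with drug return reported".
3. "If no visit with drug return reported exists, exposure duration will be set to 1 day".

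Part of the sentence introducing the definition is missing from the public text, but these three steps are complete. None of them uses dispensing dates, dose records, attended visits or last contact.

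Other sections show that such evidence exists:

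- SAP 6.1.6.1 itself tabulates dose at each visit, and the planned listings include one titled Dose Administration.
- SAP 6.1.6.2 describes a form that dates every bottle dispensed and every bottle returned.
- SAP 6.1.1 lists the dates of last dose and last contact.
- SAP 5.1.1 admits to the safety population only subjects with clinic contact after dosing.

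Protocol 9.5 allows a capsule count to be entered as not available when drug is not brought back.

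**The concern.** Long-term exposure is what this trial is meant to deliver. Its size is justified by the numbers of subjects treated for at least 26 weeks and at least 1 year (Protocol 12.1; SAP 3.2.1). An imputation that turns months of documented treatment into a single day produces a wrong value for that subject, and the SAP's own tables could contradict each other. The same subject could appear at a dose level at Weeks 4, 12 and 26 in the dosing table (14.1.8.1.2) and with 1 day in the exposure table (14.1.8.1.1).

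The treatment of the same gap is also inconsistent within SAP 6.1.6. Under 6.1.6.2, an unreturned bottle makes compliance for that visit missing. Under 6.1.6.1, the absence of any return becomes a definite value of 1 day. Subjects who drop out of contact are the likeliest to lack both a last-dose date and a return, so any error would not fall at random.

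There is a possible knock-on effect in SAP 6.3.1, where the onset-window denominator is "the total number of subjects with exposure to drug as of the first day of the window". If that uses the imputed duration, a subject set to 1 day who has an event on Day 60 is in the window's numerator but not its denominator.

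**Working it through.** The plan gives no figure to reproduce here, so the check applies its rule to its own visit schedule.

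**Inputs.** Visits on Days 28, 84 and 182 (SAP 3.2), then every 90 days (Table 1 footnote in the protocol synopsis: "These visits will be scheduled 90 (± 5) days following the previous visit"), giving Days 272, 362 and 452. First dose is taken as Day 1. Exposure = last − first + 1.

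**1-day rule (no last-dose date, no recorded return).** Loss = (true days − 1) / true days.

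| True days | Recorded | Lost |
|---|---|---|
| 84 | 1 | 83/84 = 98.8% |
| 182 | 1 | 181/182 = 99.5% |
| 365 | 1 | 364/365 = 99.7% |

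**Return-visit rule, drug returned on schedule.** The worst case is a true last dose on the day before the next planned visit.

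| Last return | True last dose | Lost |
|---|---|---|
| Day 28 | Day 83 | 55/83 = 66% |
| Day 84 | Day 181 | 97/181 = 54% |
| Day 182 | Day 271 | 89/271 = 33% |
| Day 272 | Day 361 | 89/361 = 25% |
| Day 362 | Day 451 | 89/451 = 20% |

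With the ±5-day windows the longest gap is 187 − 79 = 108 days between Weeks 12 and 26, and 90 + 5 = 95 days after Week 26.

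**Return-visit rule, returns stop early but treatment runs 365 days.** Last return on Day 28 loses 337/365 = 92%; on Day 84, 281/365 = 77%; on Day 182, 183/365 = 50%.

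**Trial level.** The share of subjects reaching the 1-day rule is not in the documents, so 1% to 10% is an assumed range. For subjects treated to Day 182, loss = share × N × 181/365.

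| Share | N = 350 (Protocol 12.1) | Person-years lost |
|---|---|---|
| 1% | 3.5 | 1.7 |
| 5% | 17.5 | 8.7 |
| 10% | 35 | 17.4 |

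With the 550 enrolled in SAP 3.2.1 the range is 5.5 × 181/365 = 2.7 to 55 × 181/365 = 27.3. If every subject truly had 365 days, mean exposure would be 365 − share × 364: 361.4 days at 1%, 346.8 at 5% and 328.6 at 10%.

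**After the change.** A subject with dosing recorded at Days 28, 84 and 182 and no return would have 182 days instead of 1. A subject who returns drug at every visit would keep the same date as now.

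**The case against.** The strongest reply is that the rule will rarely operate. It needs both a missing last-dose date and no return at any visit. Drug is collected at every visit from Visit 2 on (Table 1) and must be handed back on discontinuation (Protocol 9.6.1). Missing values are queried (SAP 5.3), and the data undergo full source verification (Protocol 14.4). The not-available entry in Protocol 9.5 concerns one capsule count and does not imply subjects who never return anything. This stands, and it is why the effect is probably small.

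It can also be said that the rule is conservative, crediting no exposure without drug accountability, and that the analysis is descriptive with no exposure-adjusted rates planned. This stands only in part: 1 day is not a cautious estimate when the dose table shows the subject on drug at Week 26.

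The other evidence has limits too. The sample diary is completed only for missed doses, illness or changes, and SAP 6.1.6.2 ranks it below drug accountability. A dispensing date shows supply, not intake. The content of the Dose Administration listing is known only from its title. These points shape the fix.

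A reader might infer three stronger things that the documents do not support:

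- **That both fallbacks remove most exposure.** With scheduled returns, the return-visit rule does so only when the last return was at Week 4 or Week 12.
- **That annual reports lose a large amount.** SAP 5.4 says "interim reports of safety data accrued will be prepared annually" but not that this rule applies to continuing subjects. An average shortfall of 45 days each, 350 × 45/365 = 43 person-years, would require all 350 to be still on treatment. Ending exposure at the last visit with confirmed dosing would leave that shortfall in place.
- **That the rule causes a one-year shortfall.** A last return on Day 362 gives 362 days because of the 90-day visit spacing, and the documents do not define one year as 365 days.

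**Conclusion.** The 1-day default is a defect in a stated rule and should be changed. For an affected subject treated to Day 84 or beyond, at least 98.8% of exposure is lost, against evidence recorded elsewhere in the same trial. The return-visit fallback is a lesser matter: at most about one visit interval when drug comes back on schedule, and more only if returns stop early while treatment continues. It can also err upward. A subject who stopped on Day 40 and returned drug on Day 84, with no last-dose date, is credited with 84 days.

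The trial-level size, about 1.7 to 17 person-years for 350 subjects at Week 26, rests wholly on the assumed 1% to 10%.

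It is tempting to conclude that the 26-week and 1-year counts and the onset-window denominators are therefore understated. That follows only if they are built on this variable. The SAP does not say so, the window definitions are not visible in the public text, and discontinuation before Week 26 is counted separately in disposition (SAP 6.1.1).

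**What to change.** In SAP 6.1.6.1, delete the 1-day rule and replace the handling of a missing last-dose date with this order:

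1. Use a known stop date if one is recorded, from the action taken for an adverse event or from disposition.
2. Otherwise use the later of the last visit with drug return and the last attended visit at which the dose record shows the subject still taking study drug.
3. Treat the diary and the dispensing date as supporting evidence only.
4. Keep 1 day only where there is no evidence of dosing after Day 1.

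Use the same end date in the onset-window denominators of SAP 6.3.1, state whether the 26-week and 1-year counts use it, and report how many end dates were imputed.

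The cost is one revised paragraph and a small programming change on data already collected. The downside is that a few subjects may be credited with slightly more exposure than they took; the count of imputed dates shows how many could be affected. The change does not remove the shortfall of up to one visit interval for subjects whose last evidence of dosing is a scheduled visit.

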6.1.6.2 Compliance

Compliance by Dispense/Return

Treatment compliance will be measured on the basis of a capsule count by the investigator or designee every time drug supplies are returned. Each subject will be instructed to bring the study medication (with the capsules that remain) with him/her to the next scheduled visit. If the subject fails to bring the study medication on the designated day, he/she will be told to bring the study medication within the next 3 days. If the subject fails to do so, the capsule count will be recorded as "not available."

The clinic will fill out the 'Dispense/Return Study Medication' Form, included in the eCRF book. This form will list each bottle dispensed, along with the bottle number, the date the bottle was dispensed, and the dose strength. This form will also list each bottle that was returned, along with the bottle number, the date the bottle was returned, along with the number of capsules returned.

Based on this form, percent compliance will be calculated using the number of capsules dispensed minus the number of capsules returned, divided by the number of capsules intended to be taken.

Average compliance will be summarized descriptively by visit, and for the study overall. The compliance for each visit is derived by the following. As an example, consider bottles dispensed at Visit X:

- 1) The expected number of capsules will be determined as the difference between the last return date for all bottles dispensed at the given visit and the Visit X date. The expected capsules calculation takes into account if >1 capsule is taken daily.
- 2) The capsules that were **assigned at the scheduled visit X** and not any unscheduled visit between visit X and the next scheduled visit are used in the calculation for Visit X

3) If any bottle from Visit X is not returned/data is not available, the number of capsules returned is not countable and per the protocol will be classified as "not available". The compliance for this visit will be missing in this case.

4) The compliance for Visit X will be calculated as the [number of capsules dispensed - returned]/[number expected]

A further categorical summary of compliance will be provided by visit, and for the study overall, using the following categories: <75%, $\ge75\%$ to $\le125\%$, and >125%.

Secondary Compliance by Diary

A Subject Diary will be utilized to assess compliance and collect comments regarding any important problems or issues (missed dose, reason for missing dose, disturbing signs/symptoms, etc) associated with this trial. The clinic staff will review the diary during each visit. Comments that may suggest AEs will be reviewed with the subject to determine the presence of AEs. Any missed doses will be recorded in the diary, along with the reason for the missed dose. The diary will help confirm the level of drug compliance in this study.

For each subject, based on the subject's diary data, percent compliance will be calculated based on recorded dose information divided by intended dosage. The format of the summary of diary-based compliance information will follow that of the eCRF-based mothod above. This measure of compliance is only meant to endorse the preceding more rigorous measure based on the drug accountability data, which will be collected in the eCRF.

A summary table of compliance by both Dispense/Return eCRF and Diary will be presented by Safety Group and overall.

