## 10.7. Unscheduled Visits

- Concomitant medication and physical therapy will be recorded
- AEs will be recorded
- Study drug dose may be adjusted per Sections 9.2.2 and 9.2.3
- Study medication collected and reviewed for compliance
- Study medication will be dispensed as required
- The next trial visit will be scheduled

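### The SAP's capsule-count compliance rule mishandles any interval with an unscheduled dispensing: depending on when the old bottles come back, a fully adherent subject scores about 50% or part of the interval goes unmeasured

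*SAP*

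**What the plan says.** SAP 6.1.6.2 first defines compliance as capsules dispensed minus capsules returned, divided by capsules intended. Numbered steps then apply this to bottles dispensed at a scheduled Visit X.

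- **Step 1 (denominator).** The expected number is based on "the difference between the last return date for all bottles dispensed at the given visit and the Visit X date". It adds: "The expected capsules calculation takes into account if >1 capsule is taken daily". No rule covers a change in daily number within the interval.
- **Step 2 (which capsules).** Only capsules assigned at the scheduled visit "and not any unscheduled visit between visit X and the next scheduled visit are used in the calculation for Visit X".
- **Step 3.** If any Visit X bottle is not returned, compliance for that visit is missing.
- **Step 4.** The ratio is "number of capsules dispensed - returned]/[number expected".

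Results are averaged by visit and overall, and also grouped "using the following categories: <75"%, 75% to 125%, and above 125%. They appear by Safety Group and overall in Table 14.1.8.2.1.

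Protocol 10.7 provides for dose adjustment at unscheduled visits and states: "Study medication will be dispensed as required". It also lists collection of medication there, without saying whether the site keeps the bottles or hands them back. Protocol 9.5 and SAP 6.1.6.2 tell subjects to bring their medication to the next scheduled visit. A subject who forgets "he/she will be told to bring the study medication within the next 3 days".

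**The concern.** A compliance ratio is meaningful only if numerator and denominator cover the same drug over the same days. Here step 2 limits the numerator to Visit X bottles, while step 1 lets the denominator run until the last of those bottles is returned. Nothing stops or splits the expected count when a subject moves to bottles from an unscheduled visit. The wording of step 2 shows that such dispensing was foreseen.

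Two outcomes are possible, depending on how a site handles the old bottles: adherent subjects are placed in the below-75% class, or days on treatment are left unmeasured. Only subjects with an unscheduled dispensing are affected, so the error is systematic for them and does not average out within that group.

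**Working it through.** The plan states no compliance figure to reproduce. The check applies steps 1, 2 and 4 to a subject who takes every intended capsule.

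**Inputs**
- Visit days 1, 28, 84 and 182 (Protocol 7.1, SAP 3.2), giving intervals L of 27, 56 and 98 days. Later visits are 90 days apart (Protocol Table 1, footnote c).
- Late-return allowance: 3 days (Protocol 9.5, SAP 6.1.6.2).
- Assumptions: one capsule per day (dosing detail is blacked out), new bottles replace the old ones on day u of the interval, and all Visit X bottles are eventually returned (otherwise step 3 makes the value missing).

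**No unscheduled visit.** L/L = 100%. The rule works.

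**Old bottles returned at the next scheduled visit.** Capsules used from Visit X bottles = u; expected = L; compliance = u/L.

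| L (days) | Switch at mid-interval | Latest switch day giving <75% |
|---|---|---|
| 27 | 14/27 = 51.9% | 20 (20/27 = 74.1%) |
| 56 | 28/56 = 50.0% | 41 (41/56 = 73.2%) |
| 98 | 49/98 = 50.0% | 73 (73/98 = 74.5%) |
| 90 | 45/90 = 50.0% | 67 (67/90 = 74.4%) |

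**All old bottles collected at the unscheduled visit.** The last return date is day u, so compliance = u/u = 100%. The remaining L − u days are covered only by unscheduled-visit bottles, which step 2 excludes. With u = 28 and L = 56, half the interval is in no calculation.

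**Late return alone.** If the subject is already using new bottles, compliance = L/(L + 3): 27/30 = 90.0%, 56/59 = 94.9%, 98/101 = 97.0%, 90/93 = 96.8%. All stay in the 75% to 125% class.

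**With the change proposed below.** In both bottle-handling cases, with u = 28 and L = 56, the numerator is 28 + 28 = 56 and expected is 56, so compliance = 100%. For a late return with new bottles in use, the denominator is capped at L and the value is also 100%.

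**The case against.** The strongest reply is that Protocol 10.7 has medication collected at unscheduled visits. If every Visit X bottle stays at the site, numerator and denominator end on the same day and nobody is misclassified. That is right as far as it goes, but the text does not say the bottles are kept, and the general instruction is to bring medication to the next scheduled visit. If they are kept, the rest of the interval goes unmeasured, so neither reading gives a complete result.

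A reader might infer two further errors that the documents do not support.

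- **An add-on capsule.** One extra capsule per day from mid-interval, with the old bottles used throughout, would give 56/(28 + 2 × 28) = 56/84 = 66.7%. This requires the denominator to follow the new daily number while the numerator ignores the added capsules. The SAP does not state that rule. If step 2 is read as limiting both parts to Visit X capsules, the result is 56/56 = 100%. With dosing detail blacked out, an adjustment might also change strength and not capsule number.
- **Late return.** It lowers the value slightly, and only if new bottles are already in use. At the nominal post-baseline intervals it changes no class.

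It is also fair to say that little depends on this summary. Exposure duration is taken from first and last dose dates, with drug return used only when the last dose date is missing (SAP 6.1.6.1). The safety population rests on dosing and later contact (SAP 5.1.1). Diary compliance is reported as well, so disagreement could be noticed, but the SAP makes the diary secondary to the capsule count and it corrects nothing.

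**Conclusion.** The point holds as a minor defect in a stated rule. After an unscheduled dispensing, capsule-count compliance depends on when old bottles are returned as well as on what the subject took. Under one handling, a fully adherent subject who switches at mid-interval scores about 50%, and a switch in roughly the first three quarters of the interval gives a value below 75%. Under the other, the ratio is 100% but days are lost. The percentages assume one capsule per day and full replacement of the old bottles.

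The consequence is limited to the descriptive summary in Table 14.1.8.2.1. The documents give no rate of unscheduled dispensing, so the number of subjects affected cannot be estimated. A reader might conclude that the trial's exposure or safety findings are compromised; the documents do not support that, because neither exposure duration nor the safety population is defined by compliance. Nor does the SAP label anyone non-compliant; below 75% is simply its lowest class.

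**What to change.** Delete the exclusion in step 2 and define both parts of the ratio over the same period, for each scheduled interval:

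- **Numerator:** all capsules dispensed in the interval, at scheduled and unscheduled visits, minus all those returned.
- **Denominator:** expected capsules from the Visit X date to the last return of any bottle dispensed in that interval, capped at the next scheduled dispensing date or the last dose date if earlier. Use the daily capsule number recorded in the dosing data for each part of the interval.
- **Step 3:** extend the missing-value rule to bottles from unscheduled visits.

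The cost is SAP wording and programming, with no new data collection apparent. The dispense/return form, as the SAP describes it, does not carry the daily capsule number or the last dose date, so it must be merged with the dosing data and the final status form. Extending step 3 may leave a few more intervals missing.

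The cap has one small drawback: a subject who keeps using old bottles until a late return is slightly overstated. With a 3-day delay and one capsule per day, this gives (56 + 3)/56 = 105.4% for the 56-day interval and (27 + 3)/27 = 111.1% for the 27-day interval, both still within the 75% to 125% class.
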